14.2 Collection and Processing

Mayo Clinic Florida and Mayo Clinic Arizona will collect and ship all samples to Mayo Clinic Rochester for processing.

14.21 Please include the following tissue reports with specimens: Research Blood Submission Form and Research Urine Submission Form.

14.22 EDTA and Sodium Citrate Whole Blood

Collect at the following time points:

Prior to Registration (≤ 14 days)
Cycle 3 Day 1 (Prior to Treatment)
Cycle 5 Day 1 (Prior to Treatment)

Collect the following tubes of blood:

Two 5mL EDTA (purple top) tube
One Sodium Citrate (blue top) tube

Process whole blood as follows:

Centrifuge EDTA and Sodium Citrate tubes at 600g for 10 minutes

Label all cryovials with Protocol #, Patient Initials and Patient ID #, Type of Sample (EDTA plasma (4), Sodium Citrate plasma (2), EDTA buffy coat (2), Sodium Citrate buffy coat (1)).

Divide plasma from each blood tube into two cryovials, approximately 1.25 mL of plasma per tube (6 aliquots- 4 EDTA plasma and 2 Sodium Citrate aliquots).

Aliquot buffy coat from each tube into separate Cryovials.

Label two of each of the EDTA and one of the Sodium Citrate plasma aliquots PRP (Platelet Rich Plasma). Then aliquot 0.5mL of each of these aliquots into 2 cryovials (labeled EDTA PRP plasma and Sodium Citrate PRP plasma). In addition label the new aliquots with Protocol #, Patient Initials and Patient ID #, Date of Birth, and U1806.

Label the second set of EDTA and Sodium Citrate aliquots with PPP (Platelet Poor Plasma). Add 50 uL of protease inhibitor cocktail / mL of plase to each of these cryovials and mix. Centrifuge cryovials at 9000g for 5 minute to separate the platelets. Aliquot 0.5 mL of each sample into two cryovials and label with sample type (2 cryovials for EDTA PPP plasma and 2 cryovials with Sodium Citrate PPP plasma). In addition label the new aliquots with Protocol #, Patient Initials and Patient ID #, Date of Birth and U1806.

Snap freeze all aliquots (4 PRP EDTA aliquots, 2 PPP EDTA aliquots, 2 PRP Sodium Citrate aliquots, 2 PPP Sodium Citrate aliquots, 2 EDTA buffy coat, 1 Sodium Citrate buffy coat aliquot)

Store at -80C until requested.

14.23 SST Tubes of Whole Blood

Collect at the following time points:

Prior to Registration (≤ 14 days)
Cycle 3 Day 1 (Prior to Treatment)
Cycle 5 Day 1 (Prior to Treatment)

Collect the following tubes of blood:

One 8.5mL SST (black/red top) tube

Process whole blood as follows:

Centrifuge SST tube at 600g for 10 minutes.

Aliquot the serum equally between two 2mL cryovials.

Re-aliquot one of the serum tubes into 0.5 mL aliquots (~4 serum aliquots). Label the new serum aliquots with Protocol #, Patient Initials and Patient ID #, Date of Birth, U1806, and **Serum w/o inhibitor**.

With second 2mL aliquot of serum add 50 uL protease inhibitor cocktail / mL of serum and mix. Aliquot 0.50 mL of this serum into cryovials (~4 serum aliquots). Label the new serum aliquots with Protocol #, Patient Initials and Patient ID #, Date of Birth, and U1806, and **Serum w/ inhibitor**.

Store at -80C until requested.

14.24 PAXgene RNA

Collect at the following time points:

Prior to Registration (≤ 14 days)
Cycle 3 Day 1 (Prior to Treatment)
Cycle 5 Day 1 (Prior to Treatment)

Collect the following tubes of blood:

One 5mL Paxgene tube

Process whole blood per manufacturer's instructions (as follows):

Incubate blood sample for at least 2 hours at room temp to ensure cells are lysed.

Centrifuge tube for 10 minutes at 3000-5000 x g using a swing out rotor **NOTE: Tubes may break if tube adapters for round bottom tubes is not used.**

Pipet off the supernatant and discard.

Add 4mL RNase-free water to the pellet and close tube with a fresh secondary BD Hemogard closure.

Vortex the pellet until visible dissolved and centrifuge at 3000-5000 x g using a swing-out rotor.

Decant or Pipet off the supernatant and discard. **NOTE: Be sure to remove as much supernatant as possible. Remaining supernatant will inhibit lysis and dilute the lysate, thus affecting binding of RNA to PAXgene membrane.**

Add 350 μ L Buffer BR1, and vortex until pellet is visibly dissolved.

Pipet sample into 1.5mL microcentrifuge tube and add 300 μ L Buffer BR2 and 40 μ L proteinase K. **NOTE: Do not mix Buffer BR2 and proteinase K together prior to adding to sample.**

Mix by vortexing for 5 seconds, and incubate on a shaker (400-1400 rpm) for 10 minutes at 55°C.

Pipet lysate into PAXgene Shredder spin Column (lilac) and place in a 2mL processing tube. Centrifuge for 3 minutes at maximum speed (but not greater than 20,000 x g)
NOTE: Be sure that the all the lysate is transferred to the spin column.
NOTE: Some samples may flow through spin column without being centrifuged.

Transfer the supernatant that flowed through column into a fresh 1.5mL microcentrifuge tube without disturbing the pellet in the processing tube.

Add 350 μ L ethanol (96-100%) and mix by vortexing. Centrifuge briefly (1-2 seconds at 500-1000- x g) to remove drops from the sides of the tube. **NOTE: Do not centrifuge longer or RNA yield will be compromised.**

Pipet 700 μ L sample into PAXgene RNA spin column (red) and place in a 2mL processing tube. Centrifuge for 1 minute at 8000-20,000 x g.

Place the spin column in a new 2mL processing tube and discard the old processing containing flow-through.

Pipet remaining sample into the PAXgene RNA spin column, and centrifuge for 1 minute at 8000-20,000 x g. Place the spin column in a new 2mL processing tube and discard the old processing tube containing the flow-through.

NOTE: Carefully pipet the sample into the spin column and visually check that the sample is completely transferred to the spin column.

Pipet 350µL Buffer BR3 into the PAXgene RNA spin column, and centrifuge for 1 minute at 8000-20,000 x g. Place the spin column in a new 2 mL processing tube and discard the old processing tube containing the flow-through.

Add 10µL DNase I stock solution to 70uL Buffer RDD in a 1.5mL microcentrifuge tube, and mix by gently flicking the tube, and centrifuge to collect liquid at the bottom of tube.

NOTE: DNase I is especially sensitive to denaturation. Mix ONLY by gently flicking the tube. DO NOT VORTEX.

Pipet the DNase I incubation mix (80µ) directly onto the PAXgene RNA spin column membrane, and let sit at room temperature for 15 minutes. NOTE: Be sure DNase I incubation mix is placed directly onto the membrane (not on walls or the O-ring of the spin column).

Pipet 350µL Buffer BR3 into the PAXgene RNA spin column, and centrifuge for 1 minute at 8000-20,000 x g. Place the spin column in a new 2 mL processing tube and discard the old processing tube containing flow-through.

Pipet 500µL diluted BR4 Buffer to the PAXgene RNA spin column, and centrifuge for 1 minute 8000-20,000 x g. Place the spin column in a new 2 mL processing tube, and discard the old processing tube and flow-through. **NOTE: Buffer BR4 is supplied as a concentrate and must be diluted with ethanol (96-100%) prior to use. For 500µL for diluted BR4 buffer use 100µL BR4 concentrate and 400 µL ethanol.**

Add another 500µL diluted BR4 Buffer to the PAXgene spin column, and centrifuge for 3 minutes at 8000-20,000 x g.

Discard the tube containing the flow-through, and place the PAXgene RNA spin column in a new 2mL processing tube, and centrifuge for 1 minute at 8000-20,000 x g.

Discard the tube containing the flow-through, and place the PAXgene RNA spin column in a 1.5mL microcentrifuge tube and pipet 40µL Buffer BR5 directly onto the PAXgene RNA

spin column membrane, and centrifuge for 1 minute at 8000-20,000 x g to elute the RNA. **NOTE: It is important to wet the entire membrane with Buffer BR5 to achieve maximum elution efficiency.**

Repeat the elution step using the same microcentrifuge tube – Pipet 40µL Buffer BR5 directly onto the PAXgene RNA spin column membrane, and centrifuge for 1 minute at 8000-20,000 x g to elute the RNA.

Incubate for 5 minutes at 65°. **NOTE: This step denatures the RNA. Do not exceed the incubation time.**

Chill on ice.

Store at -80C until requested.

14.25 Urine

Mayo Clinic Florida and Mayo Clinic Arizona will collect and ship all samples to Mayo Clinic Rochester for processing.

Collect at the following time points:

Prior to Registration (≤14 days)
Cycle 3 Day 1 (Prior to Treatment)
Cycle 5 Day 1 (Prior to Treatment)

Collect the following:
10-15 mL Urine

Process urine as follows:

Centrifuge 3mL urine at 600g for 10 minutes.

Aliquot 1 mL into two cryovials without disturbing pellet. Label cryovials with Protocol #, Patient Initials, and Date of Birth.

On the first urine cryovial label **Urine w/o Inhibitor**, and set a side.

For the second urine aliquot, add 50 uL / mL and label **Urine w/ Inhibitor**.

Store urine aliquots at -80C until requested.

14.3 Specimen Shipping and Handling

14.31 Collection Supplies

Collection supplies should be provided at each site.

14.32 Shipping and Storage

All specimens must be collected and shipped Monday – Thursday ONLY.

Samples will be stored at -80°C and consolidated at the end of the study.

Samples will be stored at the following locations:

Mayo Clinic Rochester

Upon request samples will be shipped on dry ice via overnight courier to the appropriate Mayo institution.

14.33 Background and Methodology

Samples will be available for future correlative studies in proteomics, metabolomics, and genomics as they are developed.

Samples will be analyzed at Mayo Rochester upon request.

15.0 Drug Information

15.1 Pazopanib HCl (GW786034, Votrient®)

15.11 **Background:** Pazopanib HCl is a highly potent inhibitor of vascular endothelial growth factor (VEGF) receptor tyrosine kinases (VEGFR1, VEGFR2, and VEGFR3). Vascular endothelial growth factor receptor inhibition may block VEGF driven angiogenesis and, as a consequence, constrain tumor growth.

15.12 **Formulation:** Pazopanib is supplied by Novartis as aqueous film-coated tablets containing 200 mg and 400 mg of the free base. Both 200 mg and 400 mg tablets are oval-shaped, white and packaged in white high density polyethylene (HDPE) bottles with white plastic, induction seal and child-resistant caps. Bottles of 200 mg tablets contain 34 tablets each and bottles of 400 mg tablets contain 68 tablets each.

Tablet excipients in both tablet sizes include microcrystalline cellulose, povidone, sodium starch glycolate, and magnesium stearate. The film-coat consists of titanium dioxide, hypromellose, macrogol/polyethylene glycol 400 and polysorbate 80.

15.13 **Preparation and storage:** The intact bottles should be stored at controlled room temperature [20°C - 25°C (68°F - 77°F)]. Excursions are permitted between 15°C and 30°C (59°F and 86°F).

- 15.14 **Administration:** The medication is taken orally. Pazopanib should be taken without food, at least 1 hour before or 2 hours after a meal. Pazopanib should be taken whole with water and must not be broken or crushed. If a dose is missed, it should not be taken if it is less than 12 hours until the next dose.
- 15.15 **Pharmacokinetic information:**
- a) Absorption – Pazopanib is absorbed orally with an absolute oral bioavailability range of 13.5 to 38.9% after an 800 mg dose, with a median absolute bioavailability of 21%. Plasma concentrations of pazopanib peak from 2 to 4 hours following single dose administration. Systemic exposure to pazopanib is increased when administered with food. Administration with a high-fat or low-fat meal results in an approximately 2-fold increase in AUC and C_{max} . Pazopanib should be administered at least one hour before or 2 hours after a meal. Administration of pazopanib as a crushed tablet increases the rate and extent of oral absorption relative to administration of the whole tablet. The crushing of the tablet increases AUC by 46% and C_{max} by approximately 2-fold, but decreases t_{max} by approximately 2 hours relative to administration of the whole tablet. Consequently, it is recommended not to crush pazopanib tablets.
 - b) Distribution – Binding of pazopanib to human plasma protein in vivo was greater than 99% with no concentration dependence. Pazopanib is associated with a small volume of distribution (9.2 to 131L).
 - c) Metabolism – In vitro studies demonstrate pazopanib is metabolized by CYP3A4 with a minor contribution from CYP1A2 and CYP2C8. Patients who have AST/ALT >3 X ULN and concurrent bilirubin >2 X ULN must permanently discontinue pazopanib. Use of pazopanib is not recommended in patients with total bilirubin >3 X ULN (regardless of any ALT) due to insufficient data with this severe impairment.
 - d) Elimination – Pazopanib has a mean half-life of 30.9 hours after administration of an 800mg dose. Elimination is primarily via feces with renal elimination accounting for < 4% of the administered dose.
- 15.16 **Potential Drug Interactions: CYP3A4 Inhibitors and Inducers:** Coadministration of pazopanib with strong inhibitors of CYP3A4 (e.g., itraconazole, atazanavir, indinavir, nefazodone, nelfinavir, saquinavir, telithromycin, voriconazole, ketoconazole, ritonavir, clarithromycin) increases pazopanib concentrations and should be avoided. Grapefruit juice should be avoided as it inhibits CYP3A4 activity and may also increase plasma concentrations of pazopanib. CYP3A4 inducers such as rifampin may decrease plasma pazopanib concentrations. Pazopanib should not be used if chronic use of strong CYP3A4 inducers cannot be avoided. Please see Appendix VI for a list of strong inhibitors and inducers of CYP3A4.

CYP Substrates: Results from drug-drug interaction trials conducted in cancer patients suggest that pazopanib is a weak inhibitor of CYP3A4, CYP2C8, and CYP2D6 in vivo, but had no effect on CYP1A2, CYP2C9, or CYP2C19. Concomitant use of pazopanib with agents with narrow therapeutic windows that are metabolized by CYP3A4, CYP2D6, or CYP2C8 is not recommended. Coadministration may result in inhibition of the metabolism of these products and create the potential for serious adverse events.

Concomitant use of pazopanib and simvastatin increases the incidence of ALT elevations. If a patient receiving concomitant simvastatin develops ALT elevations, follow dosing guidelines for pazopanib or consider discontinuing simvastatin. Insufficient data are available to assess the risk of concomitant administration of alternative statins and pazopanib.

If the concomitant use of a PPI is medically necessary, the dose of pazopanib should be taken without food once daily in the evening concomitantly with the PPI. If the concomitant administration of an H₂-receptor antagonist is medically necessary, pazopanib should be taken without food at least 2 hours before or at least 10 hours after a dose of an H₂-receptor antagonist. Pazopanib should be administered at least 1 hour before or 2 hours after administration of short-acting antacids.

With concomitant use of pazopanib with lapatinib (an inhibitor of P-gp, BCRP and a weak inhibitor of CYP3A4), patients should be observed for adverse reactions and the pazopanib dose should be reduced as needed.

In vitro studies also showed that pazopanib inhibits UGT1A1 and OATP1B1. Pazopanib may increase concentrations of drugs eliminated by UGT1A1 and OATP1B1. Coadministration of pazopanib 400 mg once daily with cetuximab 250 mg/m² and irinotecan 150 mg/m² resulted in a 20% increase in systemic exposure to SN-38 (a substrate for UGT1A1 and OATP1B1).

- 15.17 **Known potential toxicities:**
Summary of adverse reactions in patients with renal cell carcinoma (RCC):
Very common: $\geq 1/10$ ($\geq 10\%$)
 Metabolism and nutrition: Anorexia
 Nervous system: Headache
 Cardiac: Bradycardia
 Vascular: Hypertension
 Gastrointestinal: Abdominal pain, diarrhea, nausea, vomiting
 Hepatobiliary: Increased ALT and AST
 Skin and subcutaneous tissue: Hair depigmentation
 General: Asthenia, fatigue

Common: $\geq 1/100$ and $< 1/10$ ($\geq 1\%$ and $< 10\%$)

Blood and lymphatic: Neutropenia, thrombocytopenia
 Endocrine: Hypothyroidism
 Metabolism and nutrition: Weight decreased
 Nervous system: Dysgeusia, transient ischemic attack
 Cardiac: Myocardial ischemia, QT prolongation
 Vascular: Epistaxis, gastrointestinal hemorrhage, hematuria, venous thromboembolic events
 Respiratory, thoracic and mediastinal: Dysphonia
 Gastrointestinal: Dyspepsia, lipase elevations
 Hepatobiliary: Hepatic function abnormal, hyperbilirubinemia
 Skin and subcutaneous tissue: Alopecia, palmar-plantar erythrodysesthesia, rash, skin depigmentation
 Renal and urinary: Proteinuria
 General: Chest pain

Uncommon: $\geq 1/1,000$ and $< 1/100$ ($\geq 0.1\%$ and $< 1\%$)

Nervous system: Ischemic stroke
 Cardiac: Cardiac dysfunction (such as a decrease in ejection fraction and congestive heart failure), myocardial infarction, Torsade de Pointes
 Vascular: Cerebral hemorrhage, pulmonary hemorrhage
 Gastrointestinal: Gastrointestinal perforation, gastrointestinal fistula

Laboratory Abnormalities: $\geq 15\%$

Leukopenia, neutropenia, thrombocytopenia, lymphocytopenia, ALT increased, AST increased, glucose increased, total bilirubin increased, phosphorus decreased, calcium decreased, sodium decreased, potassium increased, creatinine increased, magnesium decreased, glucose decreased.

Summary of adverse reactions in patients with soft tissue sarcoma (STS):**Very common: $\geq 1/10$ ($\geq 10\%$)**

Metabolism and nutrition: Anorexia, weight decreased
 Nervous system: Dizziness, dysgeusia, headache
 Cardiac: Bradycardia
 Vascular: Hypertension
 Respiratory, thoracic and mediastinal: Cough, dyspnea
 Gastrointestinal: Abdominal pain, diarrhea, nausea, stomatitis, vomiting
 Skin and subcutaneous tissue: Alopecia, exfoliative rash, hair depigmentation, palmar-plantar erythrodysesthesia, skin depigmentation

Musculoskeletal and connective tissue: Musculoskeletal pain, myalgia

General: Chest pain, fatigue, peripheral edema

Common: $\geq 1/100$ and $< 1/10$ ($\geq 1\%$ and $< 10\%$)

Endocrine: Hypothyroidism

Cardiac: Cardiac dysfunction, myocardial infarction, QT prolongation

Vascular: Epistaxis, gastrointestinal hemorrhage, pulmonary hemorrhage, venous thromboembolic events

Respiratory, thoracic and mediastinal: Dysphonia, pneumothorax

Gastrointestinal: Dyspepsia

Hepatobiliary: Increased ALT and AST

Skin and subcutaneous tissue: Dry skin, nail disorder

General: Chills, blurred vision

Uncommon: $\geq 1/1,000$ and $< 1/100$ ($\geq 0.1\%$ and $< 1\%$)

Nervous system: Ischemic stroke

Vascular: Cerebral hemorrhage, hematuria

Gastrointestinal: Gastrointestinal fistula

Hepatobiliary: Hyperbilirubinemia

Skin and subcutaneous tissue: Rash

Renal and urinary: Proteinuria

General: Asthenia

Laboratory Abnormalities: $\geq 15\%$:

Leukopenia, neutropenia, thrombocytopenia, lymphocytopenia, anemia, ALKP increased, ALT increased, AST increased, albumin decreased, glucose increased, total bilirubin increased, sodium decreased, potassium increased.

Post Marketing Adverse Drug Reactions

Very common: $\geq 1/10$ ($\geq 10\%$)

Musculoskeletal and connective tissue: Arthralgia

Common: $\geq 1/100$ and $< 1/10$ ($\geq 1\%$ and $< 10\%$)

Infections and infestations (with or without neutropenia)

Gastrointestinal: Flatulence

Hepatobiliary: Gamma-glutamyl transpeptidase increased

Musculoskeletal and connective tissue: Muscle spasms

Uncommon: $\geq 1/1,000$ and $< 1/100$ ($\geq 0.1\%$ and $< 1\%$)

Blood and lymphatic system: Thrombotic microangiopathy (including thrombotic thrombocytopenic purpura and hemolytic uremic syndrome), polycythemia

Eye: Retinal detachment/tear

Gastrointestinal: Pancreatitis

Rare: $\geq 1/10,000$ and $< 1/1,000$ ($\geq 0.01\%$ and $< 0.1\%$)

Nervous system: Posterior reversible encephalopathy syndrome

Respiratory, thoracic and mediastinal: Interstitial lung disease/pneumonitis

- 15.18 **Drug procurement:** Pazopanib HCl (GW786034) is an investigational agent that will be supplied by Novartis. See Appendix V for detailed drug ordering instructions/form.
- 15.2 Nursing Guidelines for pazopanib
- 15.21 Pazopanib should be taken without food (1 hour before or 2 hours after a meal). Should be taken whole with water and not broken or crushed. If a dose is missed, do not take if it is less than 12 hours until the next dose.
- 15.22 There are numerous drug to drug interactions between pazopanib and other agents metabolized through the P450 system. Assess patient's concomitant medications, including OTC and herbal products. Refer to appendix for medications that should be avoided or used concomitantly with caution.
- 15.23 Hypertension is the most commonly reported side effect. Monitor blood pressure closely per study guidelines. Administer antihypertensives as ordered by MD.
- 15.24 Inform patient of possible changes in hair color.
- 15.25 Gastrointestinal side effects are common (diarrhea, nausea, vomiting, loss of appetite). Treat symptomatically and assess for effectiveness.
- 15.26 Due to the similarity in nature of this agent to other VEGF inhibitors (bevacizumab, VEGF-trap, etc.) monitor for signs of bleeding, thrombosis and PE. Instruct patient to report any calf tenderness, shortness of breath, chest pain or bleeding immediately.
- 15.27 Cytopenias are common. Monitor CBC w/diff and instruct patient to report any unusual bruising or bleeding and/or signs of infection to study team.
- 15.28 Monitor LFT's. Patients who have AST/ALT levels > 3x ULN and concurrent bilirubin >2X ULN should permanently discontinue pazopanib. Patients with AST/ALT levels as above and mild hyperbilirubinemia (with suspected or known Gilbert's syndrome) should be monitored weekly while continuing pazopanib.
- 15.29 Cardiac side effects (CHF, MI, chest pain, etc). while rare can be serious and life threatening. Instruct patient to report any cardiac symptoms to study team immediately.
- 15.29a RPLS, CVA, and TIA are uncommon, but are life threatening. Instruct patient to report any neurological symptoms to the study team immediately.

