 - History of abdominal fistula, gastrointestinal perforation, or intra-abdominal abscess ≤ 28 days prior to registration.
 - Clinically significant gastrointestinal abnormalities that may affect absorption of investigational product including, but not limited to:
 - Malabsorption syndrome
 - Major resection of the stomach or small bowel.
- 3.29c Corrected QT interval (QTc) > 480 msec using Bazett's formula.
- 3.29d Receiving any medications or substances with risk of torsades de pointes (see Appendix II). Note: medications or substances on the list "Drugs with Risk of Torsades de Pointes" are prohibited. Medications or substances on the list "Drugs with Possible or Conditional Risk of Torsades de Pointes" may be used while on study with extreme caution and careful monitoring.
- 3.29e Known endobronchial lesions and/or lesions infiltrating major pulmonary vessels and/or hemoptysis in excess of 2.5 mL (or one half teaspoon) ≤ 8 weeks of registration
- 3.29f Treatment with any of the following anti-cancer therapies: radiation therapy, surgery or tumor embolization, chemotherapy, immunotherapy, biologic therapy, investigational therapy or hormonal therapy ≤ 14 days prior to registration.
- 3.39g Prior autologous or allogeneic organ or tissue transplantation.
- 3.39h Elective or planned major surgery to be performed during the course of

the trial.

- 3.39i Receiving any medications or substances that are **strong or moderate inhibitors** of CYP3A4 (for a listing of medications or substances see Appendix VI).

Use of the following strong or moderate inhibitors are prohibited ≤ 7 days prior to registration.

- 3.39j Receiving any medications or substances that are **inducers** of CYP3A4 (for a listing of medications or substances see Appendix VI).

Use of inducers are prohibited ≤ 7 days prior to registration.

4.0 Test Schedule	Active Monitoring Phase					
	≤28 days prior to registration	≤14 days prior to registration	Day 1 ⁴ , Every cycle	On interval weeks 2, 6, 10	Every other cycle	End of treatment
Tests and procedures						
Informed Consent	X					
History and exam, Wt, PS			X			X
Adverse event assessment			X			
Height		X				
Pregnancy test		X ²				
Vital Signs, including temperature		X	X			X
Echo (2D M-Mode)	X ^R				X ⁸	
Hematology CBC with diff, platelets		X	X ^{R,6}			X
Chemistries ¹		X	X ^{R,6}	X ⁹		X
UPC Urine		X				
Thyroid Function Test (TSH)		X ^R			X ^R	
Coagulation Test: PT, PTT		X	X			
CT Head/MRI		X ^R				

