Appendix V

Appendix VI**Inhibitors of CYP3A4**

Strong Inhibitors of CYP3A4
> 5-fold increase in the plasma AUC values or more than 80% decrease in clearance
Indinavir (Crixivan®) Nelfinavir (Viracept®) Ritonavir (Norvir®) Clarithromycin (Biaxin®, Biaxin XL®) Itraconazole (Sporanox®) Ketoconazole (Nizoral®) Nefazodone (Serzone®) Saquinavir (Fortovase®, Invirase®) Telithromycin (Ketek®)
Moderate Inhibitors of CYP3A4
> 2-fold increase in the plasma AUC values or 50-80% decrease in clearance
Aprepitant (Emend®) Erythromycin (Erythrocin®, E.E.S. ®, Ery-Tab®, Eryc®, EryPed®, PCE®) Fluconazole (Diflucan®) Grapefruit juice Verapamil (Calan®, Calan SR®, Covera-HS®, Isoptin SR®, Verelan®, Verelan PM®) Diltiazem (Cardizem®, Cardizem CD®, Cardizem LA®, Cardizem SR®, Cartia XT™, Dilacor XR®, Diltia XT®, Taztia XT™, Tiazac®)

Inducers of CYP3A4

Inducers of CYP3A4
Efavirenz (Sustiva®) Nevirapine (Viramune®) Carbamazepine (Carbatrol®, Eptitol®, Equetro™, Tegretol®, Tegretol-XR®) Modafinil (Provigil®) Phenobarbital (Luminal®) Phenytoin (Dilantin®, Phenytek®) Pioglitazone (Actos®) Rifabutin (Mycobutin®) Rifampin (Rifadin®) St. John's wort

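### Appendix VI omits voriconazole and atazanavir, two of the strong CYP3A4 inhibitors that Section 15.16 says to avoid, so an appendix lookup finds them only under a caution rule

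*Combined protocol and SAP*

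**What the plan says.** Four places in the combined protocol and SAP bear on this.

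- **Section 15.16 (drug interactions)** states that taking pazopanib with "strong inhibitors of CYP3A4 (e.g., itraconazole, atazanavir, indinavir, nefazodone, nelfinavir, saquinavir, telithromycin, voriconazole, ketoconazole, ritonavir, clarithromycin) increases pazopanib concentrations and should be avoided". It names 11 drugs as examples and closes the topic with "Please see Appendix VI for a list of strong inhibitors and inducers of CYP3A4".
- **Exclusion 3.39i** bars patients receiving strong or moderate CYP3A4 inhibitors and points to the same appendix ("for a listing of medications or substances see Appendix VI"). It adds "Use of the following strong or moderate inhibitors are prohibited ≤ 7 days prior to registration", but no list follows at that place, so Appendix VI is the only listing it offers.
- **Exclusion 3.29d with Appendix II** deals with torsades risk. Drugs in the first Appendix II table are prohibited. Drugs in the second table (possible or conditional risk) "may be used while on study with extreme caution and careful monitoring".
- **Section 15.22 (nursing guidelines)** warns that "There are numerous drug to drug interactions between pazopanib and other agents metabolized through the P450 system" and then sends staff to an appendix, without saying which, for drugs to avoid or to use with caution.

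**The concern.** Appendix VI is the reference list for both the entry criterion and the on-treatment instruction, yet it is shorter than the examples in the section that refers to it. Staff who check a new prescription against the appendices, as 15.22 directs, will not find voriconazole or atazanavir among the CYP3A4 inhibitors. They will find them in the Appendix II caution table, and 3.29d then tells them that use is possible.

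The question can arise during treatment. Section 7.4 allows 12 months of therapy, and Section 9.3 provides for treating newly diagnosed conditions. According to 15.16 the result would be raised pazopanib concentrations. Section 15.17 lists ALT and AST increases as very common, QT prolongation as common and torsade de pointes as uncommon in renal cell carcinoma, so avoidable extra exposure bears on recognised risks.

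**Working it through.** No power or error-rate figure is involved. The check compares lists: each drug named in 15.16 against the Appendix VI strong-inhibitor list and the two Appendix II tables.

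| Drug named in 15.16 | Appendix VI strong list | Appendix II |
|---|---|---|
| Atazanavir | absent | caution table |
| Voriconazole | absent | caution table |
| Itraconazole | listed | caution table |
| Ketoconazole | listed | caution table |
| Ritonavir | listed | caution table |
| Telithromycin | listed | caution table |
| Clarithromycin | listed | prohibited table |
| Indinavir | listed | not named |
| Nefazodone | listed | not named |
| Nelfinavir | listed | not named |
| Saquinavir | listed | not named |

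**Missing from Appendix VI.** 11 − 9 = 2 drugs, and 2/11 = 18%. Neither drug is in the moderate-inhibitor list (aprepitant, erythromycin, fluconazole, grapefruit juice, verapamil, diltiazem) or in the inducer list, so they have not been filed under another heading of that appendix.

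**Status in Appendix II.** Caution 6, prohibited 1, not named 4; 6 + 1 + 4 = 11. Of the 6 with caution status, 4 are also in Appendix VI as strong inhibitors and 2 are not. Only for those 2 does a search of all the appendices return caution and nothing stricter.

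**Is Appendix VI marked as incomplete?** No. Both Appendix II tables carry a note that they are not exhaustive. Appendix VI carries none, so a reader may take absence from it as clearance.

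**Which of the two matters in practice?** Exclusion 3.23 keeps out patients known to be HIV positive, which makes atazanavir nearly moot. Voriconazole is the practical case.

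**Entry and treatment separately.** At entry, 3.39i bars strong and moderate inhibitors as a class, so both drugs are excluded although unlisted. During treatment, 15.16 names both as drugs to avoid, while 3.29d speaks of use on study for the table that contains them. No sentence says which governs.

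**The case against.** The strongest reply is that no rule is missing. Section 15.16 names both drugs, gives its names only as examples and refers to a list without calling it complete. Exclusion 3.39i works by class. An incomplete list under a class rule is then an editorial gap. This stands, and it limits the point to a list error. It does not remove the error, because Appendix VI is the listing that both provisions cite and it carries no warning that it is partial.

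A reader might infer something stronger: that the protocol contradicts itself for 6 of the 11 drugs (55%), since six strong inhibitors have caution status. The documents do not support this, for three reasons.

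- The wording of 3.29d, and the title and introduction of the Appendix II table, are framed around torsades and QT prolongation. A QT caution and a CYP3A4 instruction to avoid can both be obeyed, with the stricter one governing.
- Four of the six are listed in Appendix VI as strong inhibitors, so anyone who checks both appendices sees the warning.
- The Appendix II introduction itself names drugs that inhibit metabolism as an added risk factor.

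A reader might also say that the Appendix II table permits use. It does not: it asks for extreme caution and careful monitoring. The permission is in 3.29d.

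The harm is also limited. Exclusions 3.23 (immunocompromised patients, other than through corticosteroid use) and 3.25 (ongoing or active infection) make some need for these drugs less likely at the start, though they do not prevent conditions that arise later. An EKG and chemistries on day 1 of each cycle, liver tests at weeks 2, 6 and 10, and the QTc and liver rules in 8.3 and 8.4 would help to detect a problem. They act after exposure and do not correct the lookup.

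**Conclusion.** The point holds as a minor safety-list error with an unstated order of precedence. Two of the 11 strong inhibitors named in 15.16 (18%) are missing from the appendix that 15.16 and 3.39i cite, and one of them, voriconazole, is a realistic on-treatment case. It is not a contradiction across six drugs, and no rule is absent.

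The verdict rests on two assumptions: that some staff will consult the appendices without rereading 15.16, and that the Appendix VI list in the available text is complete. It shows no sign of a gap. The documents do not say how many of the 39 planned patients might need either drug, so the clinical effect cannot be quantified. The primary endpoint, significance level, power and analysis are unaffected.

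**What to change.** Three edits are enough.

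1. Add voriconazole and atazanavir to the strong-inhibitor list in Appendix VI.
2. Mark that list as not exhaustive, as the Appendix II tables already are.
3. Add one sentence to 3.29d and to the Appendix II caution table, for example: *This permission concerns QT risk only; it does not override 3.39i at entry or the Section 15.16 instruction on strong CYP3A4 inhibitors during treatment.*

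The cost is two drug names, one note and one sentence in two places. The edits restate 3.39i and 15.16 and create no new restriction. Moderate inhibitors should keep their present on-treatment status. Fluconazole, for instance, is barred at entry by 3.39i and has caution status in Appendix II, but the 15.16 instruction on strong inhibitors does not reach it. Sample size, visits and analysis do not change.
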